Official Title: Investigating the Immunomodulatory Effects of Esmolol in Sepsis Management and Its Impact on Patient Outcomes

NCT Number: Pending

Study Duration: January 2020 to December 2021.

Funding Source:

Sichuan Provincial Healthcare Commission - Popularization Application Project (21PJ081); and the Sichuan Cadre Healthcare Scientific Research Project (General Subject Program) (Sichuan Cadre Research 2021-207).

Principal Investigator: [name]

Affiliation: Sichuan Provincial People's Hospital

Address: [name]

Contact Information:

Email: [contact]

[contact]

Document Date: March 2, 2024

Study Protocol

Title: Esmolol in Sepsis Management: Evaluating Immunomodulatory Effects and Impact on Patient Outcomes

Objective: Evaluate the effectiveness of esmolol, a selective β 1-adrenergic receptor blocker, in modulating immune responses and improving patient outcomes in sepsis.

Background: Sepsis remains a significant challenge in intensive care with high mortality rates and complex pathophysiology involving the immune system and sympathetic nervous system (SNS) interactions. This study investigates the efficacy of esmolol in modulating immune responses and improving patient outcomes in sepsis.

Methodology:

- **Study Design:** Single-center prospective controlled study comparing patient groups treated with either standard care or standard care plus esmolol based on clinical suitability and heart rate levels.
- **Participants:** 105 patients diagnosed with sepsis or septic shock, admitted to the MICU/RICU of Sichuan Provincial People's Hospital from January 2021 to December 2022, with informed consent obtained.
- **Procedures:**
 - Random assignment of patients to treatment groups.
 - Continuous monitoring and adjustment of esmolol dosage to maintain target heart rate.
 - Collection of data on inflammatory markers, immune function, hemodynamics, and clinical outcomes.
- **Ethics Approval:** Granted by the Ethics Committee of Sichuan Provincial People's Hospital.

Statistical Analysis Plan

- **Data Analysis Strategy:**
 1. Descriptive Statistics: Summarize participant characteristics using means \pm standard deviations for continuous variables and frequencies for categorical variables.
 2. Effectiveness Evaluation: Perform logistic regression to evaluate the impact of esmolol on survival rates and clinical outcomes. Kaplan-Meier survival analysis with Log-rank test for comparing survival rates between treatment groups.
 3. Comparison Between Groups: Use independent samples t-tests or Mann-Whitney U tests for continuous variables and chi-square tests for categorical variables to compare the esmolol and control groups across different measures.
 4. Correlation Analysis: Assess the relationship between baseline immune function markers and treatment response using Pearson's or Spearman's correlation coefficients, depending on data distribution.

Software: Statistical analysis will be conducted using SPSS version 25.0 or a similar statistical package.

Ethical Considerations: Data will be anonymized to protect patient confidentiality, with all procedures carried out in accordance with the Declaration of Helsinki.

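### Does the mismatch between the stated study duration and the admission period undermine the survival analysis?

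*Protocol*

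**What the plan says.** The cover information of the Protocol carries the line "Study Duration: January 2020 to December 2021". Under Methodology, the Study Design item calls the trial a "Single-center prospective controlled study", and the Participants item describes "105 patients diagnosed with sepsis or septic shock", "admitted to the MICU/RICU of Sichuan Provincial People's Hospital from January 2021 to December 2022".

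The Effectiveness Evaluation item of the Statistical Analysis Plan section names logistic regression for survival and clinical outcomes, together with "Kaplan-Meier survival analysis with Log-rank test for comparing survival rates between treatment groups". It gives no follow-up horizon and no calendar date at which observation closes. The cover information also reads "NCT Number: Pending" and "Document Date: March 2, 2024".

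**The concern.** A prospective study cannot go on admitting patients for a year after it has ended. Set-up time could explain a 2020 start without any patients, but it does not explain admissions in 2022. Both lines therefore cannot be true of the period in which patients took part.

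The step from there to the analysis is what gives the point its apparent weight. A survival analysis needs an end of observation for patients still alive, and the only study-end date in this document is the one on the cover. If that date were used for censoring, every 2022 admission would have a negative survival time. Moving one line by a year removes the visible conflict but leaves the study ending in the month of the last admission, so late entrants would have almost no observation time. With registration pending, a wrong date could also reach the registry entry.

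**Working it through.** **Inputs.** Stated duration: January 2020 until December 2021 (cover). Admissions: January 2021 until December 2022 (Participants). Sample: 105 (Participants). Document date: 2 March 2024 (cover). Month-ends are taken as the last day of the month.

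**Step 1: compare the two periods.** Length = 12 × (end year − start year) + (end month − start month) + 1.
- Duration: 12 × 1 + 11 + 1 = 24 months.
- Admissions: 12 × 1 + 11 + 1 = 24 months.
- Overlap: January to December 2021 = 12 months.
- Admission months after the stated end: 24 − 12 = 12.

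The contradiction is confirmed. The number of patients concerned is not stated, so it lies anywhere from 0 to 105. Under an assumed even accrual it would be 105 × 12/24 = 52.5, about half.

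**Step 2: try the possible corrections.**

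| Correction | Study duration | Admissions | Months from last admission month to study end |
|---|---|---|---|
| Duration, both years +1 | Jan 2021–Dec 2022 | Jan 2021–Dec 2022 | 0 |
| Admissions, both years −1 | Jan 2020–Dec 2021 | Jan 2020–Dec 2021 | 0 |
| Duration, end year only +1 | Jan 2020–Dec 2022 | Jan 2021–Dec 2022 | 0 |
| Admissions, end year only −1 | Jan 2020–Dec 2021 | Jan 2021–Dec 2021 | 0 |

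The periods coincide only when both years of one line move. In all four cases the study end falls in the last admission month.

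**Step 3: what censoring at the stated end would do.** Days available = stated end − admission date.
- As written (31 December 2021): −1 for an admission on 1 January 2022, −365 for one on 31 December 2022.
- After any correction in the table: 30 for an admission on 1 December of the final year, 0 for one on 31 December.
- Patients without a full horizon if observation closed on that day, with even accrual over 730 days: 105 × 28/730 = 4.0 (3.8%) for an assumed 28 days; 105 × 90/730 = 12.9 (12.3%) for an assumed 90 days.

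**Step 4: does any planned analysis use that date?** Kaplan-Meier time for a patient is the date of death or last observation minus that patient's starting date. The calendar end of the study enters only through an administrative censoring rule tied to it, and the document contains none. A fixed horizon from admission, or observation until discharge, would not need one. The logistic regression, the group comparisons and the correlations use no calendar date. The figure of 105 is stated without an accrual rate or a calculation that depends on the study's length.

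**Step 5: timing of the document.** From 31 December 2022 to 2 March 2024 is 365 + 31 + 29 + 2 = 427 days; from 31 December 2021 it is 427 + 365 = 792 days. The document post-dates both periods. That does not show which line is right, but an analyst working after that date would have patients' own admission and outcome dates to use instead of a cover line.

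**The case for a change.** The strongest case for a change is that the conflict is explicit. Reading the duration as the enrolment period does not help, because the two lines would then give two different enrolment periods; and a separate statistical analysis plan could define follow-up but could not make both lines true. Correcting only a year would also hide the mismatch without saying when observation ended. Stating the first admission, the last admission and the end of follow-up would cost a line or two, and with registration pending the right dates could still be used there.

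The contradiction stands, and so does the observation that each correction ends the study in the last admission month. The rest does not carry the weight placed on it. The cover line is undefined: it sits directly above the funding source and may denote the project or enrolment period. In the latter case, ending in the last admission month is normal. The missing end of follow-up is an omitted detail of a kind commonly left to the statistical analysis plan, not a second date that conflicts with the first. Negative survival times would require an analyst to censor patients at a date before they were admitted, which any data check would expose. What will be entered in the registry cannot be judged from this document.

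**Conclusion.** The two lines disagree by one year, and 12 of the 24 admission months fall after the stated study end. At least one line is wrong if the duration is meant to cover patient participation; the document does not show which. This is a clerical slip that the sponsor can settle from the admission records, carrying the same dates into the registration. It gives no reason to exclude any patient.

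No change to the plan follows, because nothing analytical depends on the answer: the sample of 105, the tests and the survival method are the same under either correction. The losses of about 4 or 13 patients' full follow-up rest on three assumptions that the document does not make: even accrual, a 28- or 90-day horizon, and observation closing on the stated end date. Stating the end of follow-up would be helpful but is optional here.

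### The protocol gives two conflicting allocation rules, selection by suitability and heart rate and random assignment, so it is undetermined whether its unadjusted comparisons can support its effectiveness objective

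*Protocol*

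**What the plan says.** Under Methodology, Study Design, the protocol describes a controlled (not a randomised) prospective study "comparing patient groups treated with either standard care or standard care plus esmolol based on clinical suitability and heart rate levels". Two bullets later, Procedures begins with "Random assignment of patients to treatment groups". Participants mentions diagnosis, admitting unit, dates and consent; neither suitability nor heart rate appears there as an entry criterion.

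The Objective opens with "Evaluate the effectiveness of esmolol". In the Statistical Analysis Plan, item 2 uses logistic regression to "evaluate the impact of esmolol on survival rates and clinical outcomes", together with "Kaplan-Meier survival analysis with Log-rank test for comparing survival rates between treatment groups". Item 3 adds t or Mann-Whitney tests for continuous variables and "chi-square tests for categorical variables to compare the esmolol and control groups across different measures".

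**The concern.** The two statements put different things in charge of treatment. In one, a patient's condition decides who gets esmolol; in the other, chance does. The same tests mean different things under each.

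- **Random allocation.** The groups are comparable in expectation, and an unadjusted difference estimates the effect of assignment to esmolol.
- **Selection by suitability and heart rate.** The tests still compare the groups, but patients judged suitable may have had a different prognosis to begin with. A survival or immune difference could then reflect who was chosen.

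The direction cannot be read from the document: selection could flatter esmolol or hide a benefit. At stake is whether the study can answer its effectiveness question at all with the unadjusted tests listed.

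The point does not concern covariates in the logistic model, which the document neither names nor excludes. Nor is it a complaint about missing randomisation detail. A separate SAP could add adjustment, but it could not settle how patients were in fact assigned.

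**Working it through.** **1. The two statements side by side**

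| Place | What decides treatment |
|---|---|
| Methodology, Study Design | Clinical suitability and heart rate |
| Methodology, Procedures | Chance |
| Methodology, Participants | Silent; neither factor is an entry criterion |

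Both could be true if suitability and heart rate screened all patients before randomisation. No sentence says so, and Study Design attaches the two factors to the treatment received: "treated with either standard care or standard care plus esmolol based on clinical suitability and heart rate levels".

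**2. What selection could do to the unadjusted tests (illustration)**

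The protocol gives N = 105 but no event rate, allocation ratio, alpha or power, so there is no figure of its own to reproduce. Everything below except N is assumed: no true esmolol effect, half the patients at higher risk of death, equal arms (52.5 each on average), two-sided 5% chi-square test.

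Let s be the probability that a lower-risk patient receives esmolol, and 1 − s that of a higher-risk patient. With mortality m0 (lower risk) and m1 (higher risk):

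- esmolol arm: p1 = s·m0 + (1 − s)·m1
- control arm: p2 = (1 − s)·m0 + s·m1
- spurious difference: p1 − p2 = −(2s − 1)(m1 − m0)

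Worked row, s = 0.75, m0 = 0.25, m1 = 0.50:

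- p1 = 0.1875 + 0.125 = 0.3125; p2 = 0.0625 + 0.375 = 0.4375; difference −0.125
- SE under equality: √(2 × 0.375 × 0.625 / 52.5) = 0.0945
- SE under p1, p2: √((0.3125 × 0.6875 + 0.4375 × 0.5625) / 52.5) = 0.0937
- rejection rate ≈ Φ((0.125 − 1.96 × 0.0945) / 0.0937) = Φ(−0.64) ≈ 0.26; the other tail is negligible

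Simulated rejection rates (20,000 studies per row):

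| Mortality, lower / higher risk | Split s / 1 − s | Spurious difference (points) | False-positive rate |
|---|---|---|---|
| any | 50/50 (random) | 0 | 5% |
| 30% / 50% | 60/40 | −4 | 7% |
| 30% / 50% | 65/35 | −6 | 9.5% |
| 25% / 50% | 75/25 | −12.5 | 26% |
| 20% / 55% | 75/25 | −17.5 | 46% |

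If esmolol goes preferentially to higher-risk patients, the signs reverse and the rates are practically the same. The log-rank test (4,000 runs, exponential times, assumed 28-day censoring) behaves alike: 9–10% at 6 points and 26–27% at 12.5 points.

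An exact binomial calculation with other assumptions (arms 53/52, mortality 20% without and 40–50% with a prognostic factor) agrees. When the factor's prevalence differs between arms by 20, 40 or 60 points, the spurious difference is 4–6, 8–12 or 12–18 points, and the false-positive rate 7–10%, 14–25% or 27–49%.

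**3. What adjustment would cost if selection was on heart rate (illustration)**

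Assume the log-odds of receiving esmolol rise linearly with standardised heart rate. With equal arms and a between-group difference of d standard deviations, R² = d²/(d² + 4), and the standard error grows by 1/√(1 − R²). For d = 0.91: R² = 0.828/4.828 = 0.172, giving 1.10.

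| d (SD) | SE inflation | Effective sample after weighting | Propensity outside 0.1–0.9 |
|---|---|---|---|
| 0.91 | 1.10 | 84 | 2.8% |
| 1.52 | 1.26 | 59 | 27% |
| 1.90 | 1.38 | 51 | 47% |

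The last two columns come from simulation at N = 105. The effective sample depends on how weights are formed; true propensities with pooled weights give about 83, 54 and 43. The inflation formula is a linear-model one, so it is only a guide for logistic or Cox regression. A strict heart-rate cut-off would leave no overlap, and these figures would then be too optimistic.

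**The case against.** The best defence is that the Study Design phrase is loose summary wording. The protocol has little eligibility text, and this phrase may be all of it; screening on suitability and heart rate followed by randomisation would make both sentences true. That reading is possible, but it is not what is written, and Participants would be the natural place for it. It survives as one outcome of the records check, not as a reason to leave the text alone.

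Other objections stand in part:

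- The protocol states an objective, not a result, so nothing has yet been wrongly concluded. The wording is nonetheless causal.
- Logistic regression is listed first under effectiveness and might be adjusted, so the consequence is argued only for the tests that are unadjusted by nature.
- The simulations say nothing about this trial in particular. They show the possible scale, and the seriousness of the point does not rest on them.
- Patients may have been randomised, with suitability or heart rate then deciding whether assigned esmolol was given. This is a real third possibility, and the remedy must not erase a true randomisation on account of it.

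**Conclusion.** The concern holds and must be fixed. The current text makes two statements about allocation that conflict as written, on the fact that decides whether the log-rank, t or Mann-Whitney and chi-square comparisons can support a statement about effectiveness. This conclusion rests on the wording alone.

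It is not shown that the comparisons are biased; it is undetermined, and so are the direction and size of any bias. On the assumed inputs, the chi-square false-positive rate runs from close to nominal under mild selection to nearly one in two under strong selection with a strong prognostic factor.

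**What to change.** Establish from the assignment records how patients were allocated, then keep one statement and match the analysis to it.

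- **Clinicians selected treatment, or the records cannot show randomisation.** Delete the randomisation statement, label the study non-randomised, and word conclusions as association. Make the main analysis adjusted (logistic or Cox regression, or propensity weighting) for a short fixed set of recorded baseline variables: heart rate, sepsis versus septic shock, baseline hemodynamics, and a severity measure only if one was recorded. Check overlap of baseline heart rate before fitting; if it is poor, report that adjustment is not supportable rather than extrapolate. Keep the unadjusted tests as descriptive. The protocol carries "Document Date: March 2, 2024", later than both study periods it gives (2020–2021 on the front page, 2021–2022 under Participants), so label the adjustment post hoc if it was set after data collection.
- **The records show randomisation, with suitability and heart rate applied to all patients beforehand.** State these as eligibility criteria, describe the randomisation, and analyse as randomised.
- **The records show randomisation, but suitability or heart rate then decided whether assigned treatment was given.** Keep the randomisation statement, compare by assigned group, and report the departures.

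The cost is a records check and corrected wording, plus one adjusted analysis in the first case; no extra patients. The downside in the first case is a weaker causal claim and wider intervals, about 10% to 38% wider on the assumptions above, with the possibility that adjustment cannot be supported at all. In the second case only wording changes; in the third, wording, comparison by assigned group and a report of the departures.

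### The protocol defines the compared groups both by treatment given and by random assignment and sets no common start for survival, so deaths before esmolol could be counted as controls

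*Protocol*

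**What the plan says.** The Study Design item under Methodology describes a prospective controlled study "comparing patient groups treated with either standard care or standard care plus esmolol", and the same sentence goes on to make the treatment depend on suitability and heart rate. Two items later, the Procedures list gives "Random assignment of patients to treatment groups".

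The Participants item describes "105 patients diagnosed with sepsis or septic shock", who were "admitted to the MICU/RICU of Sichuan Provincial People's Hospital from January 2021 to December 2022, with informed consent obtained".

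In the section headed Statistical Analysis Plan, the Effectiveness Evaluation item has two parts: "Perform logistic regression to evaluate the impact of esmolol on survival rates and clinical outcomes", and "Kaplan-Meier survival analysis with Log-rank test for comparing survival rates between treatment groups".

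The protocol does not give a time origin for survival, a follow-up horizon, the time of esmolol start, or a rule on whether groups are analysed as assigned or as treated. It does not say how a patient is classified who was meant for esmolol but died before receiving it.

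**The concern.** The two allocation statements lead to different analysis groups. Under random assignment, a patient has a group from the moment of assignment, and an early death stays in that group. Under the design line, the group is the treatment given. Every patient has standard care, but a patient has standard care plus esmolol only once the infusion has begun, so everyone in the esmolol group has survived to that point. A patient meant for esmolol who died first has had standard care only and, taken literally, is a control.

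If follow-up begins before the esmolol start, this is immortal time bias. Early deaths can occur in one group only, and the error favours esmolol. The part of the objective about improving patient outcomes rests on this survival contrast, so a benefit could appear with no true effect.

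Randomisation alone does not prevent this. It protects the comparison only if the analysis follows the assignment, and the one line that describes the compared groups speaks of treatment given.

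**Working it through.** There is no figure in the plan to reproduce: it states no event rate, power, effect size or allocation ratio. The check therefore asks how large the bias could be under the literal reading. Only the sample size of 105 comes from the protocol; all other inputs are assumptions.

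**Simple arithmetic.** Assume no true effect, 30% overall mortality, half the patients meant for esmolol, and a share d of patients dying before esmolol could start. Per 100 patients, 50 are meant for esmolol, and 50d of them die early and move to control.

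- Esmolol mortality = (0.30 − d)/(1 − d)
- Control mortality = (50 × 0.30 + 50d)/(50 + 50d)

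| d | Esmolol | Control | Difference |
|---|---|---|---|
| 1% | 0.29/0.99 = 29.3% | 15.5/50.5 = 30.7% | 1.4 points |
| 3% | 0.27/0.97 = 27.8% | 16.5/51.5 = 32.0% | 4.2 points |
| 5% | 0.25/0.95 = 26.3% | 17.5/52.5 = 33.3% | 7.0 points |

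With 105 patients, the number moved is 52.5d: about 0.5 at d = 1% and 2.6 at d = 5%.

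**Simulation of the log-rank test.** N = 105, no true effect, 28-day horizon, and each patient meant for esmolol with probability one half. Death times are Weibull with shape k and scale constant λ = −ln(1 − m)/28^k, where m is 28-day mortality of 30%, 40% or 50%. The hazard is constant at k = 1 and front-loaded at k = 0.6. Esmolol start is exponential from the start of follow-up. Patients meant for esmolol who die before it starts count as controls. The test is a two-sided 5% log-rank with 2,000 runs per setting, and the apparent hazard ratio is exp of the mean of (O − E)/V. Ranges are over the three mortality levels.

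| Hazard | Mean delay (days) | Early deaths moved | Apparent HR | Null rejected |
|---|---|---|---|---|
| Constant | 0.25 | 0.2–0.3 | 0.97–0.99 | 4.2–5.0% |
| Constant | 1 | 0.6–1.3 | 0.90–0.92 | 5.1–6.6% |
| Constant | 2 | 1.3–2.5 | 0.83–0.85 | 7.4–9.7% |
| Constant | 3 | 2.0–3.7 | 0.78–0.79 | 10.5–13.7% |
| Front-loaded | 0.25 | 1.0–1.9 | 0.87–0.89 | 6.5–8.2% |
| Front-loaded | 1 | 2.3–4.1 | 0.75–0.76 | 11.9–17.2% |
| Front-loaded | 2 | 3.2–6.1 | 0.65–0.66 | 20.7–34.9% |
| Front-loaded | 3 | 4.2–7.7 | 0.59–0.61 | 27.9–47.6% |

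The Monte Carlo standard error near 5% is √(0.05 × 0.95/2000), about 0.5 percentage points, so the rejection rates in the first two rows differ little from nominal. The apparent hazard ratio is below 1 in every setting.

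**The same patients after the fix.** Grouped as intended and followed from the common start, the log-rank rejects in 4.1% to 6.1% of runs, close to the nominal 5%.

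**The case against.** The strongest objection is that the protocol also states random assignment, and the survival item compares treatment groups, the term the Procedures list uses for what patients are assigned to. Read together, these lines allow an as-assigned analysis in which no early death changes group. Describing arms by the treatment they receive is also ordinary trial language. This stands in part: the as-assigned reading is available, so the bias is not a stated feature of the design. But the full Study Design sentence goes on to make treatment depend on suitability and heart rate, which is more than loose naming of arms, and nothing says which line governs.

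A second objection is that time origin and analysis set are commonly left to a separate statistical analysis plan, which may exist. That also stands: a missing time origin alone would be no finding. The point rests on wording that the protocol does state, in two lines that conflict on what defines the groups. Its own statistical section does not resolve the conflict.

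Third, the size rests on assumed inputs. That is correct, and with a start within hours and a constant hazard the bias is negligible.

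A reader might go further and infer that survival is counted from ICU admission. The protocol uses admission within a calendar window to say who was eligible, not to start the clock. A reader might also infer that marker sampling is shifted in time between the groups. The protocol gives no sampling days, so nothing supports this.

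**Conclusion.** The point holds in conditional form. The protocol contradicts itself on whether groups are formed by treatment given or by random assignment, and it fixes no common start for the survival comparisons. If groups are taken as treated and survival is counted from before the esmolol start, deaths before esmolol could be counted as controls, and survival is biased towards esmolol.

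It would be too strong to say that early deaths do fall to the control group. No line says so, and the random-assignment line allows a reading in which they do not.

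Under the assumptions above, the size runs from negligible (apparent hazard ratio 0.97–0.99, rejection near 5%) to large (0.59–0.61, rejection 28–48%). Start delay and the timing of deaths decide where the trial falls, and the protocol gives neither. The correction is worth making because it is cheap and removes a bias in the favourable direction. Confidence is moderate.

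**What to change.** 1. Reconcile the Study Design and Procedures items so that the protocol gives one account of how patients were allocated.
2. In the Study Design and Effectiveness Evaluation items, define the compared groups as assigned. Keep patients assigned to esmolol who died before it or never started it in the esmolol group.
3. Count survival in both groups from the same moment: assignment, or the time the patient first met the common eligibility conditions. Starting the clock at first infusion in the esmolol group alone would not help, because deaths before infusion would still sit with the controls.
4. If patients were not randomised, or no assignment time was recorded, use a fixed landmark. Include patients alive at a set hour, group them by treatment at that hour, count survival from it, and adjust for baseline heart rate and severity. The adjustment is needed because a landmark removes immortal time but not confounding by indication, and the design line names heart rate as a basis for treatment. Choose the hour without sight of outcomes.

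The cost is a change of wording in a few items and a start date re-derived from charted times. The as-assigned analysis may slightly dilute the effect through patients who never started esmolol, and the landmark drops the few patients who died before it.

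### Survival is compared without using septic shock status, a likely prognostic factor given by the entry diagnosis; stratifying by it is a modest but worthwhile improvement

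*Protocol*

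**What the plan says.** Under Methodology, Participants, the protocol enrols "105 patients diagnosed with sepsis or septic shock". It gives no share of patients in shock and no expected mortality for either diagnosis.

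Item 2 of the analysis section (Effectiveness Evaluation) names two methods. One is a regression: "Perform logistic regression to evaluate the impact of esmolol on survival rates and clinical outcomes". Its covariates are neither listed nor excluded. The other is "Kaplan-Meier survival analysis with Log-rank test for comparing survival rates between treatment groups", with no stratification factor. Item 3 (Comparison Between Groups) reads "Use independent samples t-tests or Mann-Whitney U tests for continuous variables and chi-square tests for categorical variables"; these are two-group tests with no place for a covariate. Shock status appears in none of the analyses.

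Allocation is described in two ways. Study Design has patients receive either standard care or "standard care plus esmolol based on clinical suitability and heart rate levels". Procedures says "Random assignment of patients to treatment groups", without a ratio or a stratification factor.

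**The concern.** Sepsis and septic shock probably carry different risks of death, although the protocol does not say so. If they do, pooling them in a plain log-rank has two consequences.

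- **Precision.** Variation in risk that the entry diagnosis could explain is left in the comparison.
- **Imbalance.** If one group happens to hold more shock patients, the crude survival curves differ for that reason alone. With 105 patients an appreciable chance imbalance is not rare.

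More would be at stake if treatment followed clinical suitability. Suitability for a beta-blocker could plausibly depend on haemodynamic state, and so on shock. The imbalance would then be systematic.

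**Working it through.** **Inputs.** From the document: 105 patients, two groups, log-rank test. The document gives no alpha, power, effect size, event rate, follow-up time or shock share, so there is no stated figure to reproduce. Assumed: 53 vs 52 patients; two-sided 5% level; 28-day follow-up without dropout; exponential survival within each diagnosis; 28-day control mortality without/with shock of 15/35%, 20/40%, 20/50% and 10/50%; hazard ratios of 1, 0.5 and 0.4.

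**1. Chance imbalance under randomisation.** With K shock patients among 105, the number X in the group of 53 is hypergeometric. The imbalance is |X/53 − (K − X)/52|. Exact probabilities:

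| Shock share (K) | ≥10 points | ≥15 points | ≥20 points |
|---|---|---|---|
| 30% (32) | 29% | 9% | 2% |
| 50% (52) | 33% | 12% | 3% |
| 70% (74) | 29% | 9% | 3% |

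As a check, at a 50% share the approximate SD of the imbalance is √(0.25 × (1/52 + 1/53)) = 0.098, or 9.8 points.

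**2. What an imbalance does to crude mortality.** With no drug effect, the shift is the imbalance times the mortality gap.
- 10 points: 0.10 × 0.20 = 2 points, to 0.10 × 0.30 = 3 points.
- 20 points: 4 to 6 points.
- 40 points: 8 to 12 points.

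**3. Level and power under randomisation.** The stratified statistic is Z = Σ(O − E)/√ΣV, summed over the two diagnoses. Runs assumed 50% in shock (10,000 trials per scenario with no effect, 6,000 otherwise). With no drug effect, the unstratified test rejects in 4.6 to 5.4% of trials and so keeps its level. Power, unstratified → stratified:

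| Mortality without/with shock | HR 0.5 | HR 0.4 |
|---|---|---|
| 15/35% | 31.1 → 31.7% | 46.0 → 46.4% |
| 20/40% | 38.7 → 39.3% | 53.2 → 54.2% |
| 20/50% | 41.7 → 44.6% | 60.6 → 63.5% |
| 10/50% | 34.0 → 39.5% | 50.2 → 56.6% |

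The gain is 0.4 to 1.0 points for a 20-point gap, 2.9 points for a 30-point gap, and 5.5 to 6.4 points for an extreme 40-point gap. The smallest gains are close to simulation error.

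**4. Systematic imbalance.** Here the shock shares are fixed, esmolol vs control, with no drug effect. The splits are illustrative; the document supplies none. Two-sided rejection rates:

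| Shock share | Unstratified, 20/40% | Unstratified, 20/50% | Stratified, both |
|---|---|---|---|
| 40% vs 50% | 5.2% | 5.1% | about 5% |
| 40% vs 60% | 7.0% | 9.1% | about 5% |
| 30% vs 70% | 13% | 23% | about 5% |

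The false-benefit rate (nominal 2.5%) of the unstratified test is 4.0 to 4.2%, 6.3 to 8.8% and 12.9 to 23.3% in the three rows. Stratified, it is 2.3 to 2.6%.

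**5. Limit of step 4.** The stratified column holds only because shock is the sole confounder in those runs. The protocol itself names heart rate as a basis for treatment. Suppose a heart-rate factor with a death-rate ratio of 1.5 to 2 is split 70/30 between the groups, on top of the 40% vs 60% shock split at 20/50% mortality. The shock-stratified test then rejects about 9 to 15% of the time with no drug effect. The exact rate depends on how the baseline death rates are scaled and can be somewhat lower, but it does not return to 5%.

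**The case against.** **Strata and covariates are often left to a separate statistical analysis plan, and an unstratified log-rank is a legitimate test.** This stands for the logistic regression: that model is silent on covariates, and silence alone would be no finding. It stands less well for the survival test, because the document's own analysis section names the log-rank and the covariate-free group tests. The point is a better version of a stated method.

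**Under randomisation there is no validity problem.** This stands in full. A reader might infer that pooling inflates type I error or makes the log-rank read case mix as a drug effect. Averaged over randomisations it does neither; chance imbalance is already covered by the p-value.

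**Under suitability-based allocation the fix does not rescue the comparison.** This also stands. A reader might infer from step 4 that stratifying restores the 5% level. It would do so only if nothing but shock differed between the groups. If the shock and heart-rate imbalances pulled in opposite directions, removing one could even leave a larger net bias.

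**The bias would favour esmolol.** A reader might infer this, on the view that shock patients are judged unsuitable. The protocol does not define suitability or link it to shock, and selection on heart rate could send sicker patients to esmolol. The direction cannot be stated.

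**The change is not free.** The document is dated March 2, 2024. That is after the stated study duration (to December 2021) and after the stated admission period (to December 2022). A test chosen after outcomes have been seen is post hoc. This is a small but real downside.

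**Conclusion.** The point holds as a modest improvement. The plan does not use a likely prognostic factor that its entry diagnosis supplies.

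Under randomisation the unstratified log-rank is valid. Stratifying gains about 0.4 to 3 points of power for assumed mortality gaps of 20 to 30 points. It also protects against a chance shock imbalance, which is 10 points or more in 29 to 33% of trials.

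Under allocation by suitability and heart rate, the main problem is confounding, and the contradiction between "based on clinical suitability and heart rate levels" and "Random assignment of patients to treatment groups" is the larger defect. Stratifying then removes only the shock-driven part of the bias. The rates in step 4 show what assumed splits would do; they do not estimate the bias in this trial.

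The conclusion rests on shock being prognostic and on its being determined before allocation. The protocol states neither. All mortality, shock-share and hazard-ratio values are assumptions.

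**What to change.** 1. Reconcile the two allocation statements first. If treatment was not randomly assigned, the analysis has to deal with heart rate and the other suitability factors as well as shock.
2. Name the survival test as a log-rank stratified by septic shock (yes/no) at entry, with status fixed before allocation.
3. Name shock status as a covariate in the logistic regression.
4. Report the esmolol effect within each diagnosis descriptively, without claims from either subgroup alone.
5. If outcome data had been seen when the change was made, label it post hoc and report the unstratified log-rank beside it.

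The cost of items 2 to 5 is a few lines of text and a standard software option. The variable should be available from the entry diagnosis, and two strata among 105 patients lose little.
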